5.1. Overall Design

Part A of this study is a multicenter, randomized, double-blind, placebo-controlled, parallel-group (4 arms), weekly and once daily dose, 2-week double-blind treatment in participants with MDD. Part B of this study is a multicenter, randomized, double-blind, placebo-controlled, parallel-group (3 arms), BID dose, 2-week double-blind treatment in participants with MDD.

5.1.1. Part A

Part A of the study will include a total of 7 visits and will be approximately 5 weeks in duration:

- Up to 2-week screening period
- 2-week double-blind treatment period
- 1-week safety follow-up period

After providing written consent, participants will enter a screening period of up to 14 days. Screening procedures may be conducted on up to 2 separate dates where necessary to accommodate participant and site schedule; however, every effort should be made to conduct all procedures as early as possible in the screening period. Participants meeting the eligibility criteria at the end of Visit 2 (Day 1 of the randomized inpatient treatment) will be assigned a treatment and enter the double-blind treatment period.

Approximately 100 participants are planned for enrollment in the double-blind treatment period (25 participants each in 3 different AGN-241751 dose groups and a placebo group). Participants will be randomized in a ratio of 1:1:1:1 to 1 of 4 treatment groups: 3 mg, 10 mg, and 25 mg dose AGN-241751 and placebo. All participants will be randomized to receive active treatment or placebo (Day 1 and Days 8 to 15) and placebo alone (Days 2 through 7).

[figure not shown]
AGN-241751 is being developed for once-weekly dosing; however, the impact of repeated administration of AGN-241751 requires testing. In order to minimize participant's expectations and control for placebo response while changing dosing regimens, all treatments will be presented to participants as oral daily dosing throughout the study. On Day 1, all participants will be randomized to receive the first treatment (ie, 4 treatment groups: 3 mg, 10 mg, and 25 mg dose AGN-241751 or placebo), followed by blinded placebo on Days 2 through 7. Starting on Day 8, participants will then start 7 consecutive days of randomized treatment, administered once daily through Day 15.

On Day 1, site staff will give the participant the single dose of double-blind study treatment from Bottle 1 (for applicable visit) to take by oral ingestion in the clinic (ie, the first dose of study treatment for that week). Site staff will then give Bottle 2 (for applicable visits), which contains the single-blind placebo tablets, to the participant with the instruction to take 1 tablet daily by oral ingestion for the remainder of that week (Days 2 through 7). On Day 8, site staff will give

the participant the single dose of double-blind study treatment from Bottle 1 (for applicable visit) to take by oral ingestion in the clinic (ie, the first dose of study treatment for that week). Site staff will then give Bottle 2 (for applicable visits), which contains double-blind study treatment, to the participant with the instruction to take 1 tablet daily by oral ingestion for the remainder of that week (Days 9 through 15).

Participants will have 7 study visits during the study. The first 6 visits will occur in the following pattern: the Screening Visit (Visit 1; up to Day -14); at Visit 2 (Day 1 of the randomized inpatient treatment); at Visit 3 (1 day following the inpatient treatment day); at Visit 4 (7 days following the first inpatient treatment day, which is the 2nd inpatient treatment day); at Visit 5 (1 day following the 2nd inpatient treatment day); and at Visit 6 (7 days following the 2nd inpatient treatment day). If necessary, study visits may be conducted up to 2 days before or after the scheduled visits with the exception of visits that are 1 day apart (ie, Visits 2 and 3 must be conducted 1 day apart; and Visits 4 and 5 must be conducted 1 day apart). Participants will enter a 1-week safety follow-up period and return for Visit 7. Participants who prematurely discontinue from the study before completing the double-blind treatment should enter the 1-week safety follow-up period. Additional follow-up visits may be scheduled within 30 days, if necessary for safety reasons.

Figure 5–1 Study Design Diagram – Part A

All treatments will be presented to participants as oral once daily dosing throughout the study. Daily dosing of AGN-241751 should occur at a similar time throughout the entire study.

At Visit 2 (Day 1 of the randomized inpatient treatment), all participants will be randomized to receive the first treatment, followed by blinded placebo on Days 2 through 7.

Starting at Visit 4 (Day 8), participants will then start 7 consecutive days of randomized treatment, administered once daily through Day 15.

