 - A Patient Diary of Likert scales will be provided at Visit 12/ET (Day 14/ET) and at Visit 13 (Day 18). The Patient Diary will include Likert scales, and participants will be instructed by site staff to complete the Likert assessments at home on Days 15, 16, and 17 (between Visits 12 and 13) and on Days 19 and 20 (between Visits 13 and 14). The date and time each Likert assessment was completed are to be recorded. The Likert assessment on the day of Visit 13 will be completed by the participant in the clinic (ie, the participant will not complete the Likert assessment at home on this day).
 - Additional follow-up visits may be scheduled within 30 days of last dose of study medication or last study visit, if necessary, for safety reasons.

Study Design Diagram – Part B

Number of Participants:**Part A:**

In Part A, approximately 100 participants who meet eligibility criteria at Visit 2 (Day 1 of the randomized inpatient treatment) will be randomly assigned to study treatment such that approximately 25 participants per arm will be allocated in a 1:1:1:1 ratio.

Part B:

In Part B, approximately 120 participants who meet eligibility criteria will be randomly assigned at Visit 3 (Day 1) to receive study treatment starting on Day 1 such that approximately 40 participants per arm will be allocated in a 1:1:1 ratio. Participants who enrolled (were randomized) in Part A will not be permitted to screen into Part B (and vice versa).

Treatment Groups and Study Duration:

Part A Treatment Groups: AGN-241751 3 mg, 10 mg, and 25 mg and placebo, dosed weekly and then once daily for 14 days.

Part B Treatment Groups: AGN-241751 3 mg and 25 mg and placebo, dosed BID for 14 days.

Study Duration: approximately 5 weeks

Dosage Regimen:

Part A:

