7.1. Treatments Administered

7.1.1. Part A

On Day 1, site staff will give the participant the single dose of double-blind study treatment from Bottle 1 (for applicable visit) to take by oral ingestion in the clinic (ie, the first dose of study treatment for that week). Site staff will then give Bottle 2 (for applicable visits), which contains the single-blind placebo tablets, to the participant with the instruction to take 1 tablet daily by oral ingestion for the remainder of that week (Days 2 through 7). On Day 8, site staff will give the participant the single dose of double-blind study treatment from Bottle 1 (for applicable visit) to take by oral ingestion in the clinic (ie, the first dose of study treatment for that week). Site staff will then give Bottle 2 (for applicable visits), which contains double-blind study treatment, to the participant with the instruction to take 1 tablet daily by oral ingestion for the remainder of that week (Days 9 through 15).

Study Treatment Name	AGN-241751	Placebo
Dosage Formulation	Tablet	Tablet
Unit Dose Strengths	3 mg 10 mg 25 mg	-
Route of Administration	Oral	Oral
Dosing Instructions (Part A)	
At Day 1, the first dose from Bottle 1 (for applicable visit) given by site staff to the participant for oral ingestion in the clinic; Bottle 2 (for applicable visits) will be given to participant to take home with instructions to take 1 tablet orally every day for the rest of the week.
 
At Day 8, the first dose from Bottle 1 (for applicable visit) given by site staff to the participant for oral ingestion in the clinic; Bottle 2 (for applicable visits) will be given to participant to take home with instructions to take 1 tablet orally every day for the rest of the week.
	Same as for active treatment

Study Treatment Name	AGN-241751	Placebo
Packaging and Labeling	
Allergan will provide study treatment in the form of identically appearing tablets containing AGN-241751 doses of 3 mg, 10 mg, 25 mg, or placebo.
 
All participants will receive single-blind placebo tablets for Days 2 to 7.
	
Allergan will provide study treatment in the form of identically appearing tablets containing AGN-241751 doses of 3 mg, 10 mg, 25 mg, or placebo.

Manufacturer	Allergan, Inc.	Allergan, Inc.

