9.0 EXTENT OF EXPOSURE AND TREATMENT COMPLIANCE

9.1 EXTENT OF EXPOSURE

Exposure to the study treatment for the Safety Population during the double-blind treatment period will be summarized by treatment group (placebo, 3mg, 10mg and 25mg). Descriptive statistics (number of participants, mean, SD, median, Q1 (25 percentile), Q3 (75 percentile), minimum, and maximum) will be presented for each study day from Day 1 to Day 15.

The following parameters for the study treatment will also be summarized using descriptive statistics by treatment group:

- Treatment duration overall and by treatment regimen intervals (Day 1, Day 2-Day 7, Day 8-Day 15). Treatment duration will be calculated as the number of days from the date of the first dose of study treatment to the date of the last dose of study treatment, inclusive.

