16.0 DATA HANDLING CONVENTIONS

16.1 VISIT TIME WINDOWS

Table 16-1 presents the visits assigned for efficacy and safety analyses and the corresponding range of treatment days (window) during which an actual visit may occur.

Table 16-1 Visit Time Windows

Derived Visit	Scheduled Visit Day^a	Window
Baseline	Screening/Day 1 (Visit 2)	last nonmissing assessment before Index1 ^a
Day 2	Day 2 (Visit 3)	Days (Index1 ^a +1, IndexA ^b -1)
Day 8	Day 8 (Visit 4)	IndexA ^b
Day 9	Day 9 (Visit 5)	Days (IndexA ^b +1, IndexA ^b +4)
Day 15	Day 15 (Visit 6)	Days (IndexA ^b +5, day of final double blind visit or ET Visit occurring after IndexA ^b +5)
End of Double-Blind Treatment	The last available post-baseline assessment (unscheduled assessments) during the double-blind treatment period	
Safety Follow-up (Day 22)	Days [Day after final double-blind visit or ET visit occurring after Day 15 (Visit 6)/Early Termination visit]	

a Index1: Day of first double-blind dose

b IndexA: Day of second double-blind dose, if not received, use Index1 + 7 days

If the assessment date (if the assessment date is unavailable, use visit date instead) is on or after the date of the first dose of study treatment, the study day is calculated by assessment date – date of the first dose of study treatment + 1. If the assessment date is before the date of the first dose of study treatment, the study day is calculated by assessment date – date of the first dose of study treatment. Therefore, a negative day indicates a day before the start of the study treatment.

If a participant has 2 or more visits within the same window, the last visit with a nonmissing value will be used for analysis.

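### Part A calls Day 8 through Day 15 a 7-day daily-dosing period when it is 8 days, leaves dosing undefined when a visit shifts, and splits exposure in SAP 9.1 at fixed days

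*Protocol*

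**What the plan says.** **Length of daily dosing.** Protocol 5.1.1, the synopsis and SAP 4.0 state: "Starting on Day 8, participants will then start 7 consecutive days of randomized treatment, administered once daily through Day 15". The same protocol section gives the allocation as "active treatment or placebo (Day 1 and Days 8 to 15) and placebo alone (Days 2 through 7". It describes a clinic dose on Day 8, after which the participant is to "take 1 tablet daily by oral ingestion for the remainder of that week (Days 9 through 15". SAP 4.0 names Day 15 as the last dosing day. The synopsis, under treatment groups, describes Part A as "dosed weekly and then once daily for 14 days".

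**Visit timing.** Protocol 5.1.1 says: "If necessary, study visits may be conducted up to 2 days before or after the scheduled visits". It excepts visits that are one day apart and names the pairs Visits 2/3 and Visits 4/5. Visit 6 is Study Day 15 in the schedule (Section 2.1), but the text of 5.1.1 sets it 7 days after the second inpatient treatment day.

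**Dose timing at Visit 6.** A footnote to the schedule makes the HAM-A predose at Visit 6. No such statement is made for the MADRS at that visit. Protocol 7.6.1 monitors in-clinic dosing at Visits 4 and 6, while the schedule marks clinic administration at Visits 2 and 4.

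**Analysis.** SAP 9.1 summarizes "Treatment duration overall and by treatment regimen intervals (Day 1, Day 2-Day 7, Day 8-Day 15". SAP Table 16-1 instead anchors its visit windows on an actual dose date: "IndexA: Day of second double-blind dose, if not received, use Index1 + 7 days".

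**The concern.** Day 15 is the key secondary timepoint for repeated dosing, and Day 22 is described as 7 days after dosing ends. Both rest on a dose count that one sentence gives in two ways. The count can also vary between participants, because the visits can move and the tablet instructions do not say what happens when they do.

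Two consequences reach the analysis. Exposure by regimen can be misallocated, because SAP 9.1 cuts at calendar days while the switch to daily randomized treatment happens at a visit. On one reading of the Visit 6 window, a rating made at a permitted time is also filed under the wrong analysis visit.

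**Working it through.** **1. The plan's own figure.** Stated: 7 days, Day 8 through Day 15.
- Inclusive count: 15 − 8 + 1 = 8. The 7 is not reproduced.
- Cross-check by tablets: 1 clinic dose (Day 8) + (15 − 9 + 1) = 1 + 7 = 8 doses.
- Whole period: Day 1 (1) + Days 2–7 (6) + Days 8–15 (8) = 15 dosing days, so the synopsis's 14 does not match either.

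**2. On-schedule doses before the Day 15 score.** These are 7 if the Day 15 tablet follows the rating (1 + Days 9–14 = 1 + 6) and 8 if it precedes it. The documents do not settle which applies to the MADRS.

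**3. Doses before Visit 6 when visits shift.** Let a be the day of Visit 4 and b the day of Visit 6. If Visit 4 can move by 2 days, a runs from 6 to 10. A dose on the Visit 6 day is left out in the main columns.

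| Reading | Count | Lowest | Highest | Range with a Visit 6-day dose |
|---|---|---|---|---|
| Home tablets keep to Days 9–15 | 1 + days in 9–15 after a and before b | a=6, b=11: 1 + 2 = 3 | a=8, b=17: 1 + 7 = 8 | 4–8 |
| Dosing follows Visit 4, Visit 6 is 7 ± 2 days later | b − a | a=6, b=11: 5 | a=6, b=15: 9 | 6–10 |
| Visit 4 has no window, tablets end on Day 15 | as in the first row, a=8 | b=13: 1 + 4 = 5 | b=17: 1 + 7 = 8 | 6–8 |

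The first row also gives 3 if Visit 6 is windowed around Study Day 15 independently of Visit 4 (a=10, b=13: 1 + Days 11 and 12).

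**4. SAP 9.1 intervals against actual dosing.**
- Visit 4 on Day 6: if daily randomized treatment starts at the visit, Days 6 and 7 are randomized-treatment days but fall in the Day 2–7 placebo interval (2 days). If home tablets wait until Day 9, only the Day 6 clinic dose is misplaced.
- Visit 4 on Day 10: Days 8 and 9 come before the second double-blind dose but fall in the Day 8–15 interval (2 days).
- The misassignment is therefore up to 2 days. The second case affects 2 of the 8 days in the Day 8–15 interval.

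**5. Table 16-1 mapping.** Second-dose day + 1 to + 4 maps to Day 9, and Day 15 starts at + 5. If Visit 6 moves around Study Day 15 independently of Visit 4 (b from 13 to 17), three permitted pairs give b − a below 5: 13 − 10 = 3, 13 − 9 = 4 and 14 − 10 = 4. SAP 16.1 keeps the last nonmissing value in a window, so the Visit 6 score replaces the true Day 9 score and Day 15 is left missing. The other schedule-day pairs give 5 to 8 doses before an analysed Day 15 score when tablets keep to Days 9–15.

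**The case against.** The strongest reply is that this is mainly a wording slip. The last dosing day is consistent: the dosing text in the protocol and SAP 4.0 both say Day 15, and 22 − 15 = 7 agrees with the Day 22 description. Protocol 5.1.1 ties Visit 6 to the second inpatient dose, which puts Visit 6 no earlier than second-dose day + 5 and removes the Table 16-1 problem. Read literally, the exception for visits one day apart gives Visit 4 no window, and then SAP 9.1 misassigns nothing through a shifted Visit 4. SAP 9.1 is descriptive, and it computes duration from actual first and last dose dates. Visit shifts in a double-blind trial give no reason to expect a difference between arms.

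Much of this stands and limits the point. It does not remove it. The 7-versus-8 conflict sits within one sentence. The schedule and the text give Visit 6 two anchors. The exception can equally be read as fixing only the one-day spacing within each pair, and Table 16-1 defines the second-dose day separately from Day 8, which suggests that Visit 4 was expected to move. Even with Visit 4 fixed, the count before Visit 6 runs from 5 to 8.

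Three stronger readings are tempting but unsupported:
- A reader might infer that the Day 15 score can follow 3 to 11 daily doses. Eleven is the gap from Visit 4 on Day 6 to Visit 6 on Day 17 (17 − 6). It needs both visits to move independently and dosing to continue past Day 15, which no passage instructs; daily dosing from Day 6 to Day 15 gives 15 − 6 + 1 = 10. With Visit 4 on Day 10 and Visit 6 on Day 13, the 3-dose score is assigned to Day 9, not Day 15.
- A reader might take "take 1 tablet orally every day for the rest of the week" in the 7.1.1 dosing table to mean tablets to Day 14 only. The text above that table specifies Days 9 through 15.
- A reader might conclude that Day 22 is 8 days after the last dose. That needs a Day 14 end, which no passage states.

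**Conclusion.** The point holds in limited form. The stated 7-day period is 8 days by the plan's own day numbers, a difference of one daily dose. The number of daily doses before the Visit 6 rating is not fixed, and the three ranges above are conditional on how the documents are read; none is established as the intended schedule. The SAP 9.1 misassignment of up to 2 days requires that Visit 4 can move. The loss of a Day 15 score to the Day 9 window requires in addition that Visit 6 is windowed around Study Day 15 rather than around the second dose.

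The effect is on how the Day 15 key secondary result and the exposure tables are interpreted. The primary endpoint, MADRS change at Day 2, is not affected, and nothing here shows bias between arms.

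**What to change.** **Protocol and SAP text.** The sponsor should reconcile the passages on five matters: the number of daily doses, the last dosing day, whether the Visit 6 ratings come before or after that day's dose, what the tablet instructions mean when a visit shifts, and the two anchors for Visit 6 (Sections 2.1 and 5.1.1). Which of the conflicting statements is right is for the sponsor to decide; no dosing rule is proposed here.

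**SAP 9.1.** Replace the fixed-day regimen intervals with intervals on actual dose dates, using the index days that Table 16-1 already defines: Index1; Index1 + 1 to IndexA − 1; IndexA to the last dose. This puts the exposure summary on the same basis as the visit windows.

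**Cost.** Wording changes, and reprogramming of the exposure tables on dose dates already collected. No new data are needed.

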5.1.2. Part B

Part B of this study will include a total of 14 visits and will be approximately 5 weeks in duration as described below.

- Up to a 2-week screening period
- 2-week double-blind treatment period (Week 1 inpatient, Week 2 outpatient)
- 1-week outpatient safety follow-up period

Approximately 120 participants are planned for randomization in the double-blind treatment period (40 placebo participants, 40 AGN-241751 3 mg participants, 40 AGN-241751 25 mg participants). Eligible participants will be randomized in a ratio of 1:1:1 to one of 3 double-blind oral administration treatment groups: 3 mg dose of AGN-241751, 25 mg dose of AGN-241751, or placebo, administered BID. Participants who enrolled (were randomized) in Part A will not be permitted to screen into Part B (and vice versa).

Screening Period

After providing written consent, participants will enter a screening period of up to 14 days. Screening procedures may be conducted on up to 2 separate dates where necessary to accommodate participant and site schedule; however, every effort should be made to conduct all procedures as early as possible in the screening period. Participants will wash out of any ADT and prohibited medications under the supervision of the study investigator staff during the screening period. At Visit 2 (Day -1), study procedures required to determine eligibility will be completed prior to admission to the clinic. Participants meeting the eligibility criteria at Visit 2 (Day -1, Baseline) will be admitted to the inpatient facility, and the remainder of the Visit 2 study procedures will be completed. A urine pregnancy test should be done on Day -1 (at baseline), if more than a week has passed since the serum pregnancy test was done at Screening. Participants are required to not use any nicotine substances 1 hour prior to administration of the HVLT-R.

Double-Blind Treatment Period

Participants will be randomized in a ratio of 1:1:1 to 1 of 3 treatment groups (AGN-241751 3 mg BID, AGN-241751 25 mg BID, or placebo BID) for the 2-week double-blind treatment.

Participants will be administered 1 tablet in the morning and 1 tablet in the afternoon. At Visit 3 (Day 1), the participant will be randomized and assigned a treatment by the interactive web response system (IWRS), and the 1st dose of study medication will be administered in the morning after all predose assessments have been completed.

Week 1 Inpatient Double-Blind Treatment Period

- It is expected that participants in the double-blind treatment period will remain inpatient during the 1st week (Visit 2 to Visit 10/Discharge).
- During the inpatient treatment period, participants will have 7 visits (Visits 3 to 9); each visit will occur daily with no visit windows.
- At Visit 3 (Day 1) during the predose evaluation period, if there is a significant change (worsening or improvement in depressive symptoms) from the baseline Visit 2 (Day -1) MADRS based on the judgment of the PI, a MADRS assessment should be performed prior to the 1st dose of study medication.
- Participants will be discharged at Visit 10 (Day 8) after all predose assessments, morning dosing, and 4-hour postdose assessments are completed.
- During the inpatient treatment period, predose assessments will be performed prior to morning dosing at all inpatient visits (Visit 3 through Visit 10). Postdose assessments will be performed, as follows:
 - Visit 3 to Visit 6: 1, 2, 4, 8, and 12 hours after the morning dose (\pm 20 minutes)
 - Visit 7 to Visit 9: 4, 8, and 12 hours after the morning dose (\pm 20 minutes)
 - Visit 10: 4 hours after the morning dose (\pm 20 minutes)
- Within each timepoint, multiple assessments will be performed, as follows:
 - Assessments should be performed within \pm 20 minutes of each other
 - All psychiatric assessments (Likert Patient Depressive Symptom Scales, CSSR-S, MADRS, and CGI-S) are to be completed first prior to any other assessments (ie, qEEG, ERP) within the timepoint.
 - Participants are required to not use any nicotine substances 1 hour prior to administration of the HVLT-R.
- The afternoon dose of study medication is to be administered 8 hours (\pm 1 hour) after the morning dose.

[figure not shown]
Week 2 Outpatient Double-Blind Treatment Period

- During the outpatient treatment period, there will be 2 visits conducted every 3 days (Visit 11 [Day 11] and Visit 12 [Day 14/ET]). If necessary, these study visits may be conducted up to 1 day before or after the scheduled visit day.
- All participants who receive study medication should complete Visit 12 (Day 14/ET)
- At Visit 10 (Day 8) prior to discharge, the participant will be dispensed Bottle 2 of study medication (refer to Section 7.1.2 for dosing instruction). Participants will be instructed to bring the study medication bottle to Visit 11 for the site staff to confirm dosing compliance
- The study medication bottle will be returned at Visit 12; site staff will confirm dosing compliance.

- A Patient Diary will be provided at Visit 10 and Visit 11 for completion by the participant at home. At Visits 11 and 12, the participant will return the diary, which was provided at the prior visit. Site staff will review the diary to confirm compliance and proper completion of the diary. At Visit 11 and Visit 12, prior to leaving the clinic, the participant will be given a new diary.
- The Patient Diary will include a Study Medication Dosing Log and Likert scales.
 - Study Medication Dosing Log: Participants will be instructed by site staff to record the date and time of the Visit 10 (Day 8) afternoon dose and each subsequent dose the participant has taken (morning and afternoon) at home, inclusive of doses on days when the participant has a clinic visit (Visit 11 [Day 11] and Visit 12/ET [Day 14/ET]).
 - Likert Patient Depressive Symptom Scales: Participants will be instructed by site staff to complete the Likert assessments at home on Day 9 and Day 10 (between Visit 10 and Visit 11) and on Day 12 and Day 13 (between Visit 11 and Visit 12/ET). The date and time each Likert assessment was completed are also to be recorded. The Likert assessments on days when the participant has a clinic visit (Visit 11 [Day 11] and Visit 12 [Day 14/ET]) will be completed by the participant in the clinic (ie, the participant will not complete the Likert assessment at home on these days).

Safety Follow-Up Period (Visit 13 [Day 18] and Visit 14 [Day 21])

- Participants completing the double-blind treatment period should enter the 1-week safety follow-up period. Participants who prematurely discontinue from the study before completing 2 weeks of double-blind treatment should complete the early termination (ET) visit and then enter the 1-week safety follow-up period.
 - A Patient Diary of Likert scales will be provided at Visit 12/ET (Day 14/ET) and at Visit 13 (Day 18). The Patient Diary will include Likert scales, and participants will be instructed by site staff to complete the Likert assessments at home on Days 15, 16, and 17 (between Visits 12 and 13) and on Days 19 and 20 (between Visits 13 and 14). The date and time each Likert assessment was completed are to be recorded. The Likert assessment on the day of Visit 13 will be completed by the participant in the clinic (ie, the participant will not complete the Likert assessment at home on this day).
 - Additional follow-up visits may be scheduled within 30 days of last dose of study medication or last study visit, if necessary, for safety reasons.

Figure 5–2 Study Design Diagram – Part B

